Effect of Semi-occluded Vocal Tract Therapy on the Phonation of Children With Vocal Fold Nodules

NCT05878197

22/05/2024

Study protocol

This study was approved by the Ethics Committee of Ghent University Hospital (registration number: B670201936069) and has been registered on ClinicalTrials.gov. The consolidated standards of reporting trials (CONSORT) non-pharmacologic treatment interventions (NPT) checklist were used to report the trial specifications (Boutron et al., 2017). Written informed consent was obtained from a parent of each participant.

Participants

Children between six and 12 years old (primary school) with VFNs were eligible to participate in this study. Participants were recruited between October 2019 and January 2023 during their consultations at the voice unit of Ghent University Hospital, through flyers in other hospital departments, through social media, or by referral from voice therapists who were informed about this project. All participants were diagnosed with VFNs by an otorhinolarygologist with extensive experience in voice diagnostics ([name]). This age group was chosen because these children can cooperate with voice therapy and tolerate videolaryngostroboscopy. Exclusion criteria were a history of phonosurgery, nasal or ear diseases, neurological disorders, and parent-reported pubertal voice changes.

Design

A randomized controlled study design was used. Participants were assigned to one of the three study arms (experimental group "SP", experimental group "RVT", or the control group (CG) receiving indirect treatment), depending on their time of registration. The order in which the different voice treatments were organized was determined using a random number list. No changes in the methodology were made after trial commencement.

Voice therapy

In each study arm, a short-term, intensive, group therapy program was provided. All participants received 11 hours of voice therapy spread over four consecutive days (three hours on day 1-3 and two hours on day 4). Each group consisted of a minimum of two and a maximum of five children and was guided by one experienced voice therapist ([name] or [name]). All therapy sessions were provided at Ghent University Hospital. During the study period, participants were not allowed to attend external voice therapy.

The content and hierarchical structure of the different study arms were kept as similar as possible, with the exception of the direct vocal techniques. In the CG, no direct technique was included. Offered therapy consisted of basic education of the vocal mechanism, normal vocal function, and VFNs, vocal hygiene recommendations, posture advice, and costo-abdominal breathing exercises. Participants in the experimental groups received the same counseling and breathing exercises, combined with the direct vocal technique

SP or RVT. For SP, participants used a stainless-steel drinking straw with a diameter of 5 mm and a length of 23 cm. In each study arm, vocal rest pauses and play activities (identical for the experimental groups) were provided. Since no direct vocal technique was practiced in the CG, more play activities were scheduled in which excessive or loud voice use was being monitored and limited. Home exercises were foreseen in each study arm. Parents were not present during therapy but were informed verbally and in writing about the content of the therapy sessions so they could supervise home exercises.

Voice assessment

A standardized and multidimensional voice assessment, based on the protocol of the European Laryngological Society (Dejonckere et al., 2003) and supplemented with the acoustic voice quality index (AVQI) (Maryn et al., 2010a), was performed one day before the start of voice therapy and immediately after the last voice therapy session. A standardized pretest anamnesis by means of a semi-structured interview (see Appendix H) was used to examine the demographic characteristics, therapy history, vocal complaints, and risk factors. The assessments were performed by eight voice therapists of the Center for Speech and Language Sciences ([name], [name], [name], [name], [name], [name], [name], and [name]) with experience in voice diagnostics in two acoustically treated rooms at Ghent University Hospital. The assessors were blinded to group allocation and participants were assessed by the same assessor pre- and posttherapy. Voice assessment consisted of the following parts: (a) laryngeal anatomy and function, (b) voice quality and vocal capacities, and c) psychosocial wellbeing.

A. Laryngeal anatomy and function

Flexible videolaryngostroboscopy was performed during pretest to determine whether VFNs were present and to describe the baseline laryngeal anatomy and function in detail. In order to avoid overloading the children, videolaryngostroboscopy was performed only pretherapy. It can be perceived as an invasive examination by (young) children, therefore it was considered unethical to perform it twice over a period of five days. Flexible videolaryngostroboscopy was carried out by an experienced otorhinolaryngologist ([name], more than 25 years of experience in diagnosing voice disorders) or one of her assistants ([name] and [name]). Participants were examined in seated position with the head upright. They were asked to produce a sustained vowel [i] at habitual pitch and loudness, followed by a high-pitched [i] and a low-to-high glissando using [i]. Videolaryngostroboscopy was sometimes terminated early due to discomfort in the children, but recording the vowel [i] at normal pitch and loudness was the minimum requirement. Videolaryngostroboscopic video samples were evaluated using the Voice-Vibratory Assessment with Laryngeal Imaging (VALI) rating form (Poburka et al., 2017) and a grading scale for pediatric VFNs (Nuss et al., 2012; Shah et al., 2007). The video samples were provided with audio. An otorhinolaryngologist ([name]) and voice therapist ([name]) randomly and blindly evaluated all video samples. Both raters had experience with administering the VALI rating form, but not with the grading scale for pediatric VFNs. A half-hour training session was provided in which each parameter was clarified with the definition, a high-quality graphic, and two video examples. The raters first evaluated the video samples independently, followed by a consensus evaluation.

B. Voice quality and vocal capacities

The Dysphonia severity index (DSI) is a multiparametric index, consisting of a weighted combination of the maximum phonation time (MPT, in s), minimal intensity (Ilow, in dB), maximal frequency (fhigh, in Hz), and jitter (%) (Wuyts et al., 2000). MPT was determined by asking the children to sustain the vowel [a:] as long as possible with habitual pitch and loudness after maximum inspiration. Three measurements were performed in free field while participants were seated. Children received verbal encouragements to produce the longest possible vowel. Time was measured with a chronometer and the longest result was used for further analyses. The llow and fhigh were determined using the Voice Range Profile of the Computerized Speech Lab (CSL, model 4500, KayPENTAX, Montvale, NY) and a Shure SM-48 microphone, located at a distance of 15 cm from the mouth and angled at 45 degrees. Participants were successively asked to produce the vowel [a:] with minimal loudness and maximal pitch and they were given multiple attempts to achieve the best result. Each production was demonstrated by the assessors, who also verbally encouraged the children. Jitter % was obtained by the Multi-Dimensional Voice Program of the CSL and the same Shure SM-48 microphone. Participants were asked to count to three (an automatic sequence), followed by a sustained vowel [a:] with habitual pitch and loudness. A midvowel segment of three seconds registered with a sampling rate of 50 kHz was used for the analysis. The DSI is calculated using the following formula: 0.13 × MFT + 0.0053 × fhigh - 0.26 × Ilow - 1.18 × jitter + 12.4 (Wuyts et al., 2000). The index value usually ranges between -5 and +5. A lower index value indicates poorer voice quality or, more generally, poorer vocal functioning (Awan & Ensslen, 2010). The threshold score that distinguishes a normophonic from a dysphonic voice is +1.6 in adults (Raes et al., 2002). This threshold score was used since norm values for Dutch children are currently missing.

The Acoustic Voice Quality Index (AVQI) is an objective, multiparameter approach to quantify dysphonia severity on the basis of a sustained vowel [a:] and continuous speech (Maryn et al., 2010a). The index consists of a weighted combination of six time-domain parameters [i.e., shimmer local (SL), shimmer local decibels (SLdB), and harmonics-to-noise ratio (HNR)), frequency-domain parameters (i.e., general slope of the spectrum (slope) and tilt of the regression line through the spectrum (tilt)), and quefrency-domain parameters (i.e., smoothed cepstral peak prominence (CPPs)]. The formula of the AVQI is 2.571 (3.295 - 0.111 CPPs - 0.073 HNR - 0.213 SL + 2.789 SLdB - 0.032 slope + 0.077 tilt). The index ranges from 0 to 10 and a higher index indicates poorer voice quality. The threshold score that distinguishes a normophonic voice from a dysphonic voice in Dutch

adults is 2.95 (Maryn et al., 2010a). An Australian study suggested a threshold score of 3.46 in the pediatric population, but norm values for Dutch children are missing (Reynolds et al., 2012). In order to calculate the AVQI, the participants were asked to produce a sustained vowel [a:] at normal pitch and loudness and to read the Dutch phonetically balanced text "Papa and Marloes" (Van de Weijer & Slis, 1991). A Samson C01U Pro microphone, located at a distance of 15 cm from the mouth, and the software program PRAAT were used (Boersma & Weenink). A midvowel segment of 3 seconds of the vowel [a:] and the first two sentences of the text were combined in an automated script to calculate the AVQI. It is known that a minimum signal-to-noise ratio (SNR) of 30 dB is required to obtain acceptable perturbation measurements (Deliyski et al., 2005). For this reason, all participants with a pre- or posttest sample with an SNR less than 30 dB were removed from the analyses of the AVQI.

Consensus Auditory-Perceptual Evaluation of Voice (CAPE-V) was used for the auditoryperceptual evaluation of the children's voices (Kempster et al., 2009). This tool is designed to describe the severity of dysphonia by rating six parameters (overall severity, roughness, breathiness, strain, pitch, and loudness) on a visual-analog scale from 0 to 100, where 0 is considered within normal limits. The tool was supplemented by two additional visual-analog scales to measure asthenia and instability (Meerschman et al., 2022). Two experienced voice therapists ([name] and [name]) independently and blindly rated all the pseudonymized samples in a random order.

Afterwards, they relistened to the samples together to compare their individual evaluations and to reach a consensus. The samples consisted of the sustained vowel [a:] and the full text "Papa and Marloes," which were also used to determine the AVQI. The raters were allowed to listen multiple times to the samples. Training was not provided because both raters had experience with administering the CAPE-V. A random selection of 15% of the samples was doubled to calculate the intra-rater reliability. For this study, the CAPE-V overall severity was selected as a primary outcome parameter. The analysis of the other CAPE-V parameters can be found in Appendix I.

C. Psychosocial wellbeing

Pediatric Voice Handicap Index (pVHI). A parent completed the Dutch version of the pVHI, which is a parent-proxy tool to gain insight into the physical, functional and emotional impact of the voice disorder on their child (Veder et al., 2017). The pVHI consists of 23 items which are evaluated using a five-point Likert scale (0: never, 1: almost never, 2: sometimes; 3: almost always; 4: always). Total pVHI scores range from 0 to 92 with a higher score corresponding with a greater psychosocial impact. The same parent was asked to complete the questionnaire pre- and posttherapy.

Statistical analysis plan

The statistical analysis was performed using IBM SPSS Statistics 28 software (SPSS, Inc. Chicago, IL). The significance level was set at $\alpha = 0.05$. One-way ANOVAs were used to check for statistically significant differences in continuous parameters (e.g., age) between the three study arms. Fisher's exact tests were used for the comparison of categorical parameters (e.g., sex) between the three study arms. Pairwise comparisons with Bonferroni corrections ($\alpha < 0.016$) were performed when a significant difference was found between the groups. The inter- and intra-rater reliability of the CAPE-V overall severity has been examined with two-way mixed ICCs and their 95% confidence intervals, type consistency, single-rating, and interpreted following the classification of Koo and Li (2016) ((ICC > 0.9 'excellent'; $0.9 \ge ICC > 0.75$ 'good'; $0.75 \ge ICC > 0.5$ 'moderate'; ICC ≤ 0.5 'poor'). The effects of voice therapy were evaluated using two complementary approaches.

Firstly, a more traditional group-level analysis was conducted. Linear mixed models were used to compare groups over time on the primary outcome parameters, using the restricted maximum likelihood estimation and unstructured covariance type. Time, group, and time-by-group interaction were specified as fixed factors. A random intercept for participants was included and within-group effects of time were determined using pairwise comparisons. Unstandardized effect sizes were presented in the form of the estimated mean differences and 95% confidence intervals for the outcome variables. For the analysis of the AVQI, only participants in whom the SNR of the pretest and posttest voice samples was greater than or equal to 30 dB were selected (Deliyski et al., 2006).

Secondly, an individual-level analysis was conducted for a thorough clinical interpretation of the study results, which is not possible based on group-level average intervention effects (Sand, 2022). This individual analysis examined for each participant whether outcome parameters changed to a relevant degree or remained unchanged. Previous literature was considered to determine the magnitude of this relevant degree of change. For the DSI and AVQI, the relevant degree of change within one patient was set at 2.49 (Hakkesteegt et al., 2008) and 0.54 (Barsties & Maryn, 2013), respectively. For the pVHI and CAPE-V overall severity, the relevant degrees of change were not yet determined. Therefore, it was opted to exclude these outcome parameters from the individual analysis. The results show for DSI and AVQI what percentage of participants improved to a relevant degree, remained unchanged or deteriorated to a relevant degree. Wilson 95% confidence intervals for proportions were calculated.

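### Treatment sessions, not children, were randomised, and no concealment is described, so a child's arm may have been foreseeable and selection bias cannot be excluded

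*Combined protocol and SAP*

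**What the plan says.** The Design section of the study protocol states: "A randomized controlled study design was used". It then says that children went to SP, RVT or the control group "depending on their time of registration. The order in which the different voice treatments were organized was determined using a random number list".

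Four other places bear on the point:

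- **Participants:** "Participants were recruited between October 2019 and January 2023". Recruitment ran through the hospital's voice unit, flyers and social media, and also "by referral from voice therapists who were informed about this project".
- **Voice therapy:** treatment was given in groups. "Each group consisted of a minimum of two and a maximum of five children".
- **Laryngeal anatomy and function (part A of Voice assessment):** "Flexible videolaryngostroboscopy was performed during pretest to determine whether VFNs were present". The Voice assessment section puts the pretest one day before therapy.
- **Statistical analysis plan:** the mixed model has time, group and their interaction as fixed effects, and a random intercept for participant. It has no term for therapy session or calendar time.

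Blinding is stated for the pre/post assessors and for the raters of video and voice samples. It is not stated for those who enrolled children.

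**The concern.** When a child is randomised individually after enrolment, neither the family nor the referrer can influence the arm. Here the draw attaches to a session, and the child reaches the session through a registration date that families and referrers can influence. Whether this matters depends on what they knew when the child was booked. If the treatment of an open session was known, children who differ in severity, motivation or likely response could be booked into one arm rather than another. Blinded assessment does not prevent that. The planned baseline ANOVAs and Fisher tests cannot exclude imbalance in factors that were not measured.

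Allocation by session also means that children in one session share a treatment and a period within a recruitment window of about 39 to 40 months. The model treats them as independent. At stake are whether the between-arm contrast can be read as the effect of a randomised technique, and whether its standard error is right.

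**Working it through.** The plan gives no sample size, number of sessions or variance on this point, so it has no figure to reproduce. Group size (2 to 5) comes from the Voice therapy section and the 0.05 level from the Statistical analysis plan. Every other input below is an assumption.

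**1. Share of children who could join a known arm.** Suppose each session has one arm and that arm is known once the first child is booked. In a group of m children the share is (m − 1)/m:

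- m = 2: 1/2 = 50%
- m = 3: 2/3 = 67%
- m = 4: 3/4 = 75%
- m = 5: 4/5 = 80%
- equal mix of the four sizes: 1 − 4/(2+3+4+5) = 10/14 = 71%

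If the order is hidden until each group closes, the share is 0%. If the order is openly known, it is 100%. The documents do not say which applies.

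**2. What selection could do.** Assume 12 sessions of 3 (four per arm), unit SD and no true effect. Later registrants to the two active arms differ from other children by δ in the analysed outcome. The bias of each active-control contrast is (m − 1)/m × δ:

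- δ = 0.3: 2/3 × 0.3 = 0.20 SD
- δ = 0.5: 2/3 × 0.5 = 0.33 SD
- δ = 0.8: 2/3 × 0.8 = 0.53 SD (0.54 in simulation)

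The simulated rejection rate of the three-arm test at 0.05 was 6.6%, 10.6% and 19.8% (4,000 runs).

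These sizes require the whole difference to act on change, because the time-by-group term compares pre-to-post change. If the arms differ only in baseline severity by d, with pre-post correlation ρ, the bias in mean change is (1 − ρ)d:

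- d = 0.25: (1 − 0.8) × 0.25 = 0.05 to (1 − 0.5) × 0.25 = 0.125 baseline SD
- d = 0.5: (1 − 0.8) × 0.5 = 0.10 to (1 − 0.5) × 0.5 = 0.25 baseline SD

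**3. What calendar drift could do.** Take the same layout with no selection, session order fully permuted, and a linear drift in the outcome of 1 or 2 SD across the study (10,000 runs):

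- mean bias of the SP-control contrast: about 0.00 for both drifts
- rejection rate of the child-level test: 7.8% and 17.4%
- rejection rate when session means are analysed: 4.6% and 5.6%

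Drift therefore acts as between-session variance, and an analysis that respects the session absorbs it.

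**4. Which model term helps.** With complete pre/post data, a main effect of session date shifts both of a child's measurements equally and cancels from the change. In a numerical check the time-by-group estimate (0.15925) and its standard error (0.39596) were identical to five decimals with and without it. Only a date-by-time term acts on the change.

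**The case against.** The strongest reply is that a registration date gives no control over the arm if the order is hidden. The plan never says that recruiters, referrers or families knew the order. A reader might infer that the arm was foreseeable for most children; the documents do not support that. The 50% to 80% range rests on disclosure at the first booking, and at m = 2 it is exactly half.

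A reader might also infer that eligibility was settled with the arm in view, because stroboscopy belongs to the pretest. That a session's treatment was fixed does not mean it was known to the person deciding. The pre/post assessors were blinded, and children recruited at voice-unit consultations may already have been diagnosed. No exclusion made with knowledge of the arm is reported.

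A third inference, that allocation over calendar time biases the contrast, fails under random session order, as step 3 shows. The selection sizes in step 2 are also upper-end illustrations, since stable differences in level cancel from a change over about five days.

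These replies limit the claim but do not remove it. The allocation rule is explicit: sessions were drawn, children were not. No safeguard at enrolment is described, and the model ignores the unit that was randomised.

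**Conclusion.** The point holds in this form. The trial was randomised by session, and its description should say so. Because concealment is not described, the share of children entering a foreseeable arm lies anywhere from 0% to 100%, and is 50% to 80% if arms became known when a group opened. Selection bias is possible and unquantified. Between about 0.05 baseline SD and 0.5 SD is an illustrative span under the assumed shifts and correlations, not an estimate for this trial.

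Calendar drift causes no average bias under random order. Leaving session out of the model can still make the test too liberal: about 8% and 17% against 5%, for assumed drifts in change of 1 and 2 SD over 12 sessions of 3. Neither the number of sessions nor any drift is given in the documents.

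**What to change.** 1. **Allocation rule.** State it as follows: children fill the next session; the session list is closed, and eligibility laryngoscopy and pretest are completed, before that session's treatment is opened from a concealed list held outside recruitment. Avoid fixed blocks of three, because the last arm of each block is then certain in advance. If blocking is used, vary and conceal the block size. Recruitment ended in January 2023, so for this trial the text can only record whether these conditions were met; the rule itself serves any further recruitment.
2. **Description.** Call the trial randomised by session, not by child.
3. **Data already collected.** Report each session's date, arm and size, who held the list, and when arms were revealed to recruiters and families. Add a sensitivity analysis with session date by time (not a date main effect alone) and a therapy-group random effect on change. These terms address drift and clustering; they do not remove selection bias.
4. **Conclusion.** If the arm was known before registration for a session closed, word the between-arm result as open to selection bias.

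The cost is small: revised wording, a session table, one extra analysis and a few degrees of freedom. Under the rule in item 1, therapists would learn the treatment only about one day ahead. No additional children or visits are needed.

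### The outcome model has no age term, so if age affects response to therapy a chance age gap between arms shifts the contrast in that trial; adjustment is a cheap, optional improvement

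*Combined protocol and SAP*

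**What the plan says.** Under Participants, eligibility covers the whole primary-school range: "Children between six and 12 years old (primary school) with VFNs were eligible to participate in this study". The Design section describes no stratification by age.

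In the Statistical analysis plan, age is the named example of a continuous variable compared between arms: "One-way ANOVAs were used to check for statistically significant differences in continuous parameters (e.g., age) between the three study arms". The only stated consequence of a significant result is further baseline testing. Bonferroni-corrected pairwise comparisons "were performed when a significant difference was found between the groups".

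The group-level model is then given without covariates: "Time, group, and time-by-group interaction were specified as fixed factors". It goes on: "A random intercept for participants was included and within-group effects of time were determined using pairwise comparisons". The Voice assessment section fixes two measurement times; the assessment "was performed one day before the start of voice therapy and immediately after the last voice therapy session". Both values are responses in the model, so the comparison of groups over time is a comparison of pre-to-post change. The individual-level analysis describes no age adjustment either.

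**The concern.** A baseline test whose result cannot change the analysis gives no protection. If arms are small it is also weak evidence of balance, since a sizeable age difference can easily go undetected.

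Age could plausibly affect how much a child gains from four days of therapy: how well a technique is learned, and how far performance on the maximum-effort tasks behind the DSI improves. If so, two things follow. When one arm happens to be older, part of the age effect on change is counted as a therapy effect in that trial. In every trial, the variation in change that age could explain stays in the residual and widens the interval. Age is held for every child, so both could be dealt with at little cost.

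**Working it through.** **Inputs.** From the documents: ages 6 to 12, significance level 0.05, fixed effects of time, group and time-by-group, a random intercept per child, one pretest and one posttest. Not given: number per arm, SD of age, correlation *r* between age and change. The only size stated is that of a therapy group ("Each group consisted of a minimum of two and a maximum of five children"), which is not arm size. The plan has no design figure to reproduce. Assumed below: *n* = 8 to 30 per arm, *r* = 0 to 0.5, age uniform over 6 to 12 years (SD = 6/√12 = 1.73 years, so 0.5 SD is about 0.87 year).

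**Step 1: what cancels.** Let age act on level with slope *b* and on change with slope *g*:

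- pre = *b*·age + child effect + error
- post = *b*·age + child effect + arm effect + *g*·age + error
- change = arm effect + *g*·age + difference of errors

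With complete pairs the time-by-group estimate is the difference in mean change, so its shift is *g* × (gap in mean age), and *b* drops out. Simulated with 10 per arm, one arm 1 year older, no therapy effect, child-effect SD 1 and error SD 0.7:

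| *b* | *g* per year | time-by-group | posttest only |
|---|---|---|---|
| 0.3 | 0 | -0.002 | 0.306 |
| 0.3 | 0.05 | 0.054 | 0.359 |
| 0.3 | 0.10 | 0.100 | 0.407 |
| 0.3 | 0.20 | 0.204 | 0.501 |
| 0 | 0.10 | 0.096 | 0.090 |

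The planned contrast responds to *g* only. Fits of the mixed model to three simulated data sets agree. The estimates were 0.7094, 0.6078 and -0.4080 both without age and with an age main effect; with age-by-time added they became 0.5724, 0.5503 and -0.3831.

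**Step 2: how often a gap arises.** In SD units the difference in mean age between two arms has standard error √(2/*n*). At *n* = 10 this is 0.447, and P(|gap| > 0.5) = 2[1 − Φ(0.5/0.447)] = 2[1 − Φ(1.118)] = 0.26; simulation with uniform ages gives 0.27. At *n* = 20 the formula gives 0.11 and at *n* = 30 it gives 0.05.

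**Step 3: size of the shift.** At *n* = 10, trials with a gap above 0.5 SD have a mean gap of about 0.72 SD. The shift in SD of change is *r* × gap: 0.3 × 0.72 = 0.22 and 0.5 × 0.72 = 0.36. Simulation gives about 0.20 to 0.36 unadjusted and about zero with age in the change model. For scale, the contrast's own standard error is √(2/10) = 0.45.

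**Step 4: would the ANOVA notice?** With one arm 0.8 SD older, the non-centrality is *n*(0.533² + 2 × 0.267²) = 0.427*n*. Power at 0.05 is 0.32 (*n* = 8), 0.40 (10), 0.58 (15), 0.72 (20) and 0.89 (30). The chance that the largest of the three gaps is at least 0.5 SD while the ANOVA is non-significant is 45% at *n* = 10, 21% at 20 and 8% at 30.

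**Step 5: precision and coverage at *n* = 10.**

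- Mean 95% interval width without age: 1.82 SD of change.
- With age: 1.77 at *r* = 0.3 (3% narrower), 1.61 at *r* = 0.5 (12% narrower), 1.85 at *r* = 0 (1.85/1.82 = 1.02, about 2% wider).
- Break-even: √(1 − *r*²) × 1.85/1.82 = 1 gives *r* ≈ 0.18, so about 0.2.
- Coverage without age, over all trials: about 0.95. In trials with a gap above 0.5 SD: about 0.93 at *r* = 0.3 and 0.91 at *r* = 0.5, returning to about 0.95 with adjustment.

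**The case against.** The strongest reply is that an unadjusted analysis of a randomised trial is valid. Chance imbalance is part of what the standard error measures, and overall coverage is nominal. That stands, so the omission cannot be called overall bias. Even in the selected 27% of trials, a shift of 0.2 to 0.4 SD is smaller than the contrast's standard error of 0.45 SD.

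A reader might infer that any age difference between arms passes straight into the therapy contrast. The documents do not support this. Each child is measured before and after therapy, so age effects on level (longer phonation or a different pitch range in older children, say) cancel. The cancellation is exact with complete pairs, as in the AVQI set by construction, and approximate where a visit is missing. A posttest-only comparison would carry the full age effect, but that is not the planned contrast.

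A reader might also infer that the report will present a non-significant test as proof of balance, or that the arms are known to be small. The plan says neither. It says only that differences were checked, and it states no arm size.

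Finally, no figure in the documents shows that age modifies the response over four days. The plan chose this age range because such children can cooperate with therapy, which if anything argues against a strong effect through cooperation. This also stands: the correlation is an assumption, and below about 0.2 adjustment slightly widens the interval.

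**Conclusion.** The point holds in a limited form. The age test has no bearing on the effect analysis, and the model has no age term. If age affects response to therapy, the result is conditional bias in trials with an age gap, together with some lost precision; there is no overall bias under randomisation.

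The size rests on two assumptions the documents cannot settle: about 10 children per arm and an age-change correlation of 0.3 to 0.5. On those, roughly one trial in four has a gap above 0.5 SD between a given pair of arms, and the shift is then about 0.2 to 0.4 SD of change. At 30 or more per arm such gaps are rare and the concern fades; with no correlation there is no shift at all. The figures also take the allocation to behave as random; whether assignment by time of registration achieves that is a separate question. Severity: minor, an optional improvement.

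**What to change.** In the mixed model for each outcome, prespecify age centred on the overall mean together with its interaction with time. Centring keeps the within-group effects of time interpretable for a child of average age. An age main effect alone is not enough, because with complete pairs it leaves the time-by-group estimate unchanged. Equivalently, use a posttest model adjusted for pretest, with age as an ordinary covariate.

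Summarising age by arm descriptively in place of the significance tests would be tidier, but changes no result on its own.

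The cost is a sentence in the plan and one degree of freedom, on data already held. If age does not matter, intervals widen by about 2% at 10 per arm; a net gain in precision needs a correlation above about 0.2. The adjustment assumes one age slope on change common to all arms. Since the plan is written in the past tense, if the outcomes have already been analysed the adjusted model should be reported as a sensitivity analysis and labelled as such.
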